#### **<Chemotherapy/Immunotherapy>**

- Name of chemotherapy/immunotherapy drug: Record generic name.
- Duration of administration: Record the start date and stop date of the chemotherapy/immunotherapy.

**<Radiation therapy>**

- Site of radiation therapy: Record the site of radiotherapy.
- Duration of radiation therapy: Record the start date and stop date of the radiation therapy.

**3.5.4.7. Concomitant Medication**

The physician records the medication especially all anti-hypertensive drugs and any drug related to CYP3A4/5(including transfusion) which has been administered at the point of being enrolled in this study or which are administered newly after being enrolled. Check either 'yes' or 'no', if 'yes', record in detail.

- Name of drug: Record the name of drug.
- Total daily dose: Record the total daily dose.
- Duration of administration: Record the start date and stop date of the concomitant medication (year/ month / day). If the medication is being continued at the completion of the study, record the start date only.
- Purpose of administration: Record the purpose in detail.

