#### **3.5.4. Investigating Matters**

This means that the physician should enroll all subjects to whom INLYTA® is prescribed for the first time after contract is executed and who agree that Pfizer Korea and companies working with Pfizer Korea use his/her information by signing the 'data privacy statement'.

Data for patients who are currently on INLYTA® will be collected as much as possible following the categories for patients who are prescribed with INLYTA® for the first time.

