### 3.5.4.9. Safety

#### 3.5.4.9.1. Adverse Event

Every observed and reported adverse event, regardless of the causal relationship with the study drug, must be recorded on an adverse event section in case report forms. The query pattern of experience of adverse event to the subjects is as follow;

Patients who are prescribed with INLYTA® for the first time during the study period: “Have you had any health problem since last visit?”

Patients who are already on INLYTA® at the time of enrollment: all safety information will be collected from medical chart since the date of treatment initiation.

For adverse events repeating before and after administrating the study drug, record the date adverse event was first experienced and the date adverse event resolved. Background information on INLYTA® can be obtained from the current version of the local product document, which is the single reference safety document (SRSD) for information relating to INLYTA®.

Check either ‘yes’ or ‘no’ in adverse event section. If ‘yes’, record in detail.

- Adverse events: Record the name of adverse event. If possible, specify diagnosis, not individual symptoms. Record the name according to National Cancer Institute Common Terminology Criteria for Adverse Events (CTCAE) Version 5.0.
- Date of onset: Record the date of onset. Record approximate date if an actual date is unknown.
- Date of resolution: Record the date of resolution. Record approximate date if an actual date is unknown.
- Severity: Severity evaluation of adverse event must be done according to the NCI CTC grade.
  - The physician will use the following definitions of severity in accordance with the National Cancer Institute Common Terminology Criteria for Adverse Events (CTCAE) Version 5.0 to describe the maximum intensity of the adverse event:

Grade	Definition
Grade 1	Mild; asymptomatic or mild symptoms; clinical or diagnostic observations only; intervention not indicated.
Grade 2	Moderate; minimal, local or noninvasive intervention indicated; limiting age-appropriate instrumental ADL*.
Grade 3	Severe or medically significant but not immediately life-threatening; hospitalization or prolongation of hospitalization indicated; disabling; limiting self care ADL**.
Grade 4	Life-threatening consequences; urgent intervention indicated.
Grade 5	Death related to AE.

Activities of Daily Living (ADL)

\*Instrumental ADL refer to preparing meals, shopping for groceries or clothes, using the telephone, managing money, etc.

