\* Other causality of adverse event: If the adverse event is not related to the study drug, physicians should indicate the most appropriate cause from the followings and record in detail.

1. Disease under the study
2. Other disease (please specify)
3. Concomitant treatment drug or non-drug (please specify)
4. Others (please specify)

(5) Conditional/unclassified

- It needs more data to make an appropriate assessment or its additional data are being reviewed.

(6) Unaccessible/unclassifiable

- Lack of sufficient information or conflicting information hampers accurate causality assessment or supplementation or confirmation.

(7) Not applicable

- Action: Check relevant action.

- A. Discontinuation (Permanently, Temporarily or delayed)
- B. Dosage reduced
- C. Dosage increased
- D. No Change
- E. Unknown
- F. Not Applicable

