### **5.1.2. Reporting period**

For each patient, the safety event reporting period begins at the time of the patient's first dose of Inlyta or the time of the patient's informed consent if s/he is already exposed to Inlyta, and lasts through the end of the observation period of the study, which must include at least 28 calendar days following the last administration of a drug under study; a report must be submitted to Pfizer Safety (or its designated representative) for any of the types of safety events listed in the table above occurring during this period. If a patient was administered a drug under study on the last day of the observation period, then the reporting period should be extended for 28 calendar days following the end of observation. Most often, the date of informed consent is the same as the date of enrollment. In some situations, there may be a lag between the dates of informed consent and enrollment. In these instances, if a patient provides informed consent but is never enrolled in the study (e.g., patient changes his/her mind about participation, failed screening criteria), the reporting period ends on the date of the decision to not enroll the patient.

If the investigator becomes aware of a SAE occurring at any time after completion of the study and s/he considers the SAE to be related to Inlyta, the SAE also must be reported to Pfizer Safety.

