6.1.5. Concomitant Medication

- 1) Concomitant medication will be presented in frequency and percentage.

Statistical Analysis Plan for rPMS

- 2) Concomitant medication classified by Level 1 and Level 2 according to the latest version of ATC classification system in detail will be presented in each frequency and percentage.

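### For patients whose first INLYTA dose precedes enrolment, drugs stopped before enrolment are not recorded, although adverse events are collected and analysed from first dose

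*Protocol*

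**What the plan says.** Protocol 3.5.4.7 limits the concomitant medication record to drugs "which has been administered at the point of being enrolled in this study or which are administered newly after being enrolled", with special attention to antihypertensives, drugs related to CYP3A4/5, and transfusion. For each drug listed, the site is told: "Record the start date and stop date of the concomitant medication".

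Protocol 3.5.4.9.1 sets a different window for AEs in patients already on INLYTA: "all safety information will be collected from medical chart since the date of treatment initiation". SAP 6.2 summarises all AEs after administration and makes no cut at enrolment.

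The only general instruction for already-treated patients is in Protocol 3.5.4: "Data for patients who are currently on INLYTA® will be collected as much as possible following the categories for patients" newly prescribed the drug. It gives no look-back date.

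SAP 6.1.5 says "Concomitant medication will be presented in frequency and percentage" and adds an ATC breakdown, without naming the period covered. Concomitant medication then appears as a Yes/No factor in dummy Table 2, as ATC counts in Table 6, and as a Yes/No factor tested against AE incidence (Table 24) and objective response (Table 30). Tables 24 and 30 are produced for all patients and again for each sub-group.

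**The concern.** An enrolment anchor works for a patient who is enrolled at first dose. The study also admits patients already on treatment, and one of these may be enrolled well after first dose. In such a patient AEs are collected for the stretch between first dose and enrolment, but a drug that was stopped during it has no place on the form.

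Three uses of the data are affected.

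- The listing of co-medication (Table 6) is incomplete for these patients.
- The Yes/No factor in Tables 2, 24 and 30 refers to treatment from first dose in a patient enrolled then, and to a later-starting period in a patient enrolled later. The pooled tables mix the two.
- The protocol's causality scale turns on whether other drugs could explain the event. For early AEs, the study database may not hold the drugs needed to check that judgement afterwards.

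**Working it through.** The documents state no figure for this point, so the check sets the collection windows side by side.

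1. **AE window, patient already on INLYTA:** first dose to end of observation (Protocol 3.5.4.9.1). All such AEs are analysed (SAP 6.2).
2. **Drug window, same patient:** drugs in use at enrolment, with their own start dates, plus drugs started later (Protocol 3.5.4.7).
3. **Difference:** drugs stopped before enrolment, whether begun before or after the first INLYTA dose.

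Take a patient enrolled six months after first dose (an assumed lag).

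| Event | In the record? |
|---|---|
| Antihypertensive started in month 1, still taken at enrolment | Yes, dated from month 1 |
| CYP3A4/5 drug taken from month 1 to month 3 | No |
| Drug started in month 7 | Yes |
| AE with onset in month 2 | Yes, and analysed |

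The second drug was being taken when the AE began, and it is the one left out.

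**Who is affected.** SAP 3.4 defines Sub-group 2 by INLYTA use since before the contract date, not by enrolment. The gap therefore falls mainly on Sub-group 2, but a patient first treated after the contract date and enrolled later sits in Sub-group 1 and has the same gap.

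**Effect on the Yes/No factor.** A patient is wrongly coded No only if every relevant drug had stopped before enrolment and none was in use then or started afterwards. The error from this source runs one way: a true Yes may become No.

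**Size.** The documents give neither the lag from first dose to enrolment nor the share of short courses. Purely as an illustration, suppose short courses are spread evenly over an assumed 12 months of treatment. The share ending before enrolment is then about (enrolment month)/12: 0/12 = 0% for enrolment at first dose, 3/12 = 25% at month 3, 6/12 = 50% at month 6 and 9/12 = 75% at month 9. These are shares of short courses lost. They are not shares of patients miscoded or of AEs affected, and they do not carry over to Tables 24 or 30.

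**A related mismatch.** Protocol 5.1.2 starts the safety event reporting period, for a patient already treated, at "informed consent if s/he is already exposed to Inlyta", whereas Protocol 3.5.4.9.1 goes back to treatment initiation. The two may serve different purposes (reporting to the sponsor's safety unit and recording on the CRF), but the protocol does not say so.

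**The case against.** The strongest reply is that the gap is narrow and partly covered elsewhere.

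- Any continuing drug is captured over the early period through its start date. This stands. A reader might infer that co-medication is recorded only from enrolment, or that the drug and AE windows do not overlap before it. Section 3.5.4.7 does not support that.
- For an AE judged unrelated to INLYTA, the physician can name "Concomitant treatment drug or non-drug (please specify" as the cause. This helps, but only for AEs already judged unrelated.
- Protocol 5.1.1 requires relevant concomitant medications for serious and other 24-hour reportable events. That leaves out ordinary non-serious AEs and, on the face of 5.1.2, events before consent in patients already exposed.
- The instruction in Protocol 3.5.4 to follow the same categories as far as possible could be read as permitting a look-back. It sets no date, and Section 3.5.4.9.1 shows that where the authors wanted a first-dose anchor they wrote one. The CRF was not available and may say more, which limits certainty.
- The SAP treats concomitant medication as a subject-level flag and never links drugs to AE dates in either sub-group. This also stands, and it limits the statistical harm to possible misclassification of that flag and an incomplete listing.

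A second tempting inference is that the missing drugs bias the causality tables (20 and 21) and inflate the adverse drug reaction counts, since SAP 6.2 counts every category except Unlikely as related. The documents do not show this. The physician assigns causality, medical records are a stated data source (Protocol 3.3), and Protocol 5.1.3 requires enough information to judge every AE. Nothing confines that judgement to the concomitant medication page. What weakens is the ability to check it from the database.

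**Conclusion.** The point holds in a limited form. For anyone whose first INLYTA dose precedes enrolment, the protocol as written leaves out drugs stopped before enrolment while it collects AEs from first dose and the SAP analyses them. Table 6 is incomplete for these patients, and the Yes/No factor in Tables 2, 24 and 30 covers a different period in them and may be misclassified. Early AEs also have a thinner drug record behind them.

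The size cannot be computed from the documents; it would be nil if every patient were enrolled at first dose. The conclusion rests on reading Section 3.5.4.7 as worded and on the CRF guide not already setting a look-back. In a largely descriptive surveillance study this is not a threat to the main results, but it is a stated rule that should be corrected because the correction is cheap.

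**What to change.** 1. In Protocol 3.5.4.7 and the CRF guide, replace the enrolment anchor with one rule for all patients: record drugs in use at the first INLYTA dose, or started at any time from then to the end of observation. For patients already on INLYTA, take them from the same chart used for the AEs.
2. State the same window in SAP 6.1.5, so that Tables 2, 6, 24 and 30 refer to one period.
3. Reconcile the AE window in Protocol 3.5.4.9.1 (first dose) with the reporting period in 5.1.2 (consent for patients already exposed). If the two are meant to differ, say what each governs.

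The rule should apply to all patients rather than to Sub-group 2 alone, because that sub-group is defined by contract date. The change aligns the windows; the factor remains an ever-use flag and does not become exposure at the time of an AE.

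The cost is a sentence or so in each place and somewhat more abstraction for already-treated patients, from charts that are already reviewed back to first dose.

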**3.5.4.8. Administrative Status for Study Drug**

INLYTA® is provided by the physician's prescription and Pfizer Korea will not provide drug for this study.

Record the following with regard to administrative status for the study drug.

- Duration of administration: Record the start date and stop date of the medicated drug (year / month / day). If the medication is being continued at the completion of the study, check the box next to 'ongoing'.
- A single dose: Record the dose (in mg) of study drug. In case of dose titration up or down, record each dose with the periods respectively.
- Daily dosing frequency: Record dosing frequency per day.
- Reason for dose adjustment: Record any remarks if applicable

Refer to LPD for posology and method of administration.

### 3.5.4.9. Safety

#### 3.5.4.9.1. Adverse Event

Every observed and reported adverse event, regardless of the causal relationship with the study drug, must be recorded on an adverse event section in case report forms. The query pattern of experience of adverse event to the subjects is as follow;

Patients who are prescribed with INLYTA® for the first time during the study period: “Have you had any health problem since last visit?”

Patients who are already on INLYTA® at the time of enrollment: all safety information will be collected from medical chart since the date of treatment initiation.

For adverse events repeating before and after administrating the study drug, record the date adverse event was first experienced and the date adverse event resolved. Background information on INLYTA® can be obtained from the current version of the local product document, which is the single reference safety document (SRSD) for information relating to INLYTA®.

Check either ‘yes’ or ‘no’ in adverse event section. If ‘yes’, record in detail.

- Adverse events: Record the name of adverse event. If possible, specify diagnosis, not individual symptoms. Record the name according to National Cancer Institute Common Terminology Criteria for Adverse Events (CTCAE) Version 5.0.
- Date of onset: Record the date of onset. Record approximate date if an actual date is unknown.
- Date of resolution: Record the date of resolution. Record approximate date if an actual date is unknown.
- Severity: Severity evaluation of adverse event must be done according to the NCI CTC grade.
  - The physician will use the following definitions of severity in accordance with the National Cancer Institute Common Terminology Criteria for Adverse Events (CTCAE) Version 5.0 to describe the maximum intensity of the adverse event:

Grade	Definition
Grade 1	Mild; asymptomatic or mild symptoms; clinical or diagnostic observations only; intervention not indicated.
Grade 2	Moderate; minimal, local or noninvasive intervention indicated; limiting age-appropriate instrumental ADL*.
Grade 3	Severe or medically significant but not immediately life-threatening; hospitalization or prolongation of hospitalization indicated; disabling; limiting self care ADL**.
Grade 4	Life-threatening consequences; urgent intervention indicated.
Grade 5	Death related to AE.

Activities of Daily Living (ADL)

\*Instrumental ADL refer to preparing meals, shopping for groceries or clothes, using the telephone, managing money, etc.

\*\*Self care ADL refer to bathing, dressing and undressing, feeding self, using the toilet, taking medications, and not bedridden.

If the severity of an adverse event changed, the adverse event must be entered separately. Record stop date of previous severity and onset date of new severity – along with completion of all other items.

- Seriousness: Check either 'yes' or 'no'. If 'yes', record the appropriate number for the category of seriousness.

A serious adverse event is any untoward medical occurrence in a subject administered a medicinal or nutritional product (including pediatric formulas) at any dose that:

- (1) results in death;
- (2) is life-threatening;
- (3) requires inpatient hospitalization or prolongation of hospitalization;
- (4) results in persistent or significant disability/incapacity(substantial disruption of the ability to conduct normal life functions);
- (5) results in congenital anomaly/birth defect.

Progression of the malignancy under study (including signs and symptoms of progression) should not be reported as a serious adverse event unless the outcome is fatal within the safety reporting period. Hospitalization due to signs and symptoms of disease progression should not be reported as a serious adverse event. If the malignancy has a fatal outcome during the study or within the safety reporting period, then the event leading to death must be recorded as an adverse event and as a serious adverse event with severity Grade 5.

Lack of efficacy should be reported as an adverse event when it is associated with a serious adverse event.

Medical and scientific judgment is exercised in determining whether an event is an important medical event. An important medical event may not be immediately life-threatening and/or result in death or hospitalization. However, if it is determined that the event may jeopardize the subject or may require intervention to prevent one of the other outcomes listed in the definition above, the important medical event should be reported as serious.

Examples of such events are intensive treatment in an emergency room or at home for allergic bronchospasm; blood dyscrasias or convulsions that do not result in hospitalization; or development of drug dependency or drug abuse.

Additionally, any suspected transmission via a Pfizer product of an infectious agent, pathogenic or non-pathogenic, is considered serious. The event may be suspected from clinical symptoms or laboratory findings indicating an infection in a subject exposed to a Pfizer product. The terms “suspected transmission” and “transmission” are considered synonymous. These cases are considered unexpected and handled as serious expedited cases by PV personnel. Such cases are also considered for reporting as product defects, if appropriate.

In case of serious adverse event, Drug Safety Unit in Pfizer Pharmaceuticals Korea is to be notified promptly by the physician.

Check the following at the end of the study or after the resolution of adverse event.

- Outcome: The evaluation of outcome will include: Record the date of recovery in case of ‘Recovered’ or ‘Recovered with sequelae’.
  - Recovered
  - Recovered with sequelae
  - Recovering
  - Not recovered
  - Unknown

- Causality of adverse event to the study drug: The causal relationship of adverse event to the study drug must be allocated by the physician according to the following criteria.

(1) Certain

- It follows a reasonable time sequence from administration of the drug (before and after the study medication).
- It could not be explained by other drugs, chemical substance or accompanying diseases.
- It has clinically reasonable reaction on cessation of the drug.
- It has pharmacological or phenomenological reaction to re-administration of the drug, where necessary.

(2) Probable/likely

- It follows a reasonable time sequence from administration of the drug (before and after the study medication).
- It could not be explained by other drugs, chemical substance or accompanying diseases.
- It has clinically reasonable reaction on cessation of the drug.

(No information on re-administration)

(3) Possible

- It follows a reasonable time sequence from administration of the drug.
- It could also be explained by other drugs, chemical substance or accompanying diseases.
- It lacks information or has unclear information on discontinuation of the drug.

(4) Unlikely

- It is not likely to have a reasonable causal relationship from administration of the drug. Rather, it seems to be temporary.
- It could also be reasonably explained by other drugs, chemical substances or latent diseases.

\* Other causality of adverse event: If the adverse event is not related to the study drug, physicians should indicate the most appropriate cause from the followings and record in detail.

1. Disease under the study
2. Other disease (please specify)
3. Concomitant treatment drug or non-drug (please specify)
4. Others (please specify)

(5) Conditional/unclassified

- It needs more data to make an appropriate assessment or its additional data are being reviewed.

(6) Unaccessible/unclassifiable

- Lack of sufficient information or conflicting information hampers accurate causality assessment or supplementation or confirmation.

(7) Not applicable

- Action: Check relevant action.

- A. Discontinuation (Permanently, Temporarily or delayed)
- B. Dosage reduced
- C. Dosage increased
- D. No Change
- E. Unknown
- F. Not Applicable

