## **3. RESEARCH METHODS**

### **3.1. Study design**

Observational, non-interventional drug and multi-center study in which subjects will be administered as part of routine practice at Korean health care centers by accredited physicians. At least 3000 subjects should be enrolled in this study based on the Article 6 of “Basic Standards for the Re-examination of New Medicines” notified by MFDS. However, with additional 3 years of study period, at least 100 subjects who are being treated with Inlyta within the approved indication will be studied for total of 9 years according to the review result by the MFDS per Pfizer’s request to adjust the number of subjects. The study can be performed in Korean health care centers where INLYTA® is prescribed for advanced renal cell carcinoma (aRCC) after failure of one prior systemic therapy which is the indication for INLYTA® and where post-marketing study is allowed by institutions.

To achieve the target sample size, the study is being conducted in prospective study design and retrospective study design.

Patients to whom INLYTA® is first administered or patients who are already on INLYTA® during the study period should be enrolled in the study. Observation should be done from treatment initiation of INLYTA® for at least 28 calendar days. There are no visits or activities mandated by this study and routine observation will be done during INLYTA® treatment.

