3.1. Safety Analysis Set

Safety analysis set will be included all subjects who have been administered INLYTA® at least once and evaluated with safety-related endpoints at least once.

The case below shall be excluded from the safety analysis set in the following order:

- 1) Subjects who have been already completed for INLYTA® prior to the contract date.
- 2) Subjects who have not been administered INLYTA®.
- 3) Subjects who have not met the inclusion/exclusion criterion.
- 4) Subjects who have not been evaluated for any safety-related endpoints.
- 5) Subjects who have any significant protocol violation.

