[Table 7] Administrative status for INLYTA®

Factor	Classification	Number of subjects n(%)
Period of first administration [†]	Sub-group 1	xxx(xx.xx)
	Sub-group 2	xxx(xx.xx)
	Total	xxx(xx.xx)
Duration of administration (day)	n	xxx
	Mean±SD	xx.xx±xx.xx
	Median	xx.xx
	Min~Max	xx.xx~xx.xx
	Category 1	xxx(xx.xx)
	Category 2	xxx(xx.xx)
	Category 3	xxx(xx.xx)
	...	xxx(xx.xx)
	Total	xxx(xx.xx)
Total dose (mg)	n	xxx
	Mean±SD	xx.xx±xx.xx
	Median	xx.xx
	Min~Max	xx.xx~xx.xx
Daily average dose (mg/day)	n	xxx
	Mean±SD	xx.xx±xx.xx
	Median	xx.xx
	Min~Max	xx.xx~xx.xx
	Category 1	xxx(xx.xx)
	Category 2	xxx(xx.xx)
	Category 3	xxx(xx.xx)
	...	xxx(xx.xx)
	Total	xxx(xx.xx)

[†]Sub-group 1: Subjects who are first administered INLYTA® during the study period

Sub-group 2: Subjects who has continued administration of INLYTA® since the time prior to the contract date

Dummy Table

[Table 8] Summary of incidence of adverse events

Adverse Events	Sub-group 1 (N=xxx) n(%), [E]	Sub-group 2 (N=xxx) n(%), [E]	Total (N=xxx) n(%), [E]
Serious adverse events	xxx(xx.xx), [xxx]	xxx(xx.xx), [xxx]	xxx(xx.xx), [xxx]
Serious adverse drug reactions	xxx(xx.xx), [xxx]	xxx(xx.xx), [xxx]	xxx(xx.xx), [xxx]
Unexpected serious adverse events	xxx(xx.xx), [xxx]	xxx(xx.xx), [xxx]	xxx(xx.xx), [xxx]
Unexpected serious adverse drug reactions	xxx(xx.xx), [xxx]	xxx(xx.xx), [xxx]	xxx(xx.xx), [xxx]
Unexpected adverse events	xxx(xx.xx), [xxx]	xxx(xx.xx), [xxx]	xxx(xx.xx), [xxx]
Unexpected adverse drug reactions	xxx(xx.xx), [xxx]	xxx(xx.xx), [xxx]	xxx(xx.xx), [xxx]
Adverse events	xxx(xx.xx), [xxx]	xxx(xx.xx), [xxx]	xxx(xx.xx), [xxx]
Adverse drug reactions	xxx(xx.xx), [xxx]	xxx(xx.xx), [xxx]	xxx(xx.xx), [xxx]

Sub-group 1: Subjects who are first administered INLYTA® during the study period

Sub-group 2: Subjects who has continued administration of INLYTA® since the time prior to the contract date

E: number of adverse events

Dummy Table

[Table 9] Serious adverse events and serious adverse drug reactions

System Organ Class [§] Preferred Term	Serious adverse events		Serious adverse drug reactions	
	n(%), [E]	[95% CI]	n(%), [E]	[95% CI]
System Organ Class Preferred Term	xxx(xx.xx), [xxx] xxx(xx.xx), [xxx] xxx(xx.xx), [xxx] xxx(xx.xx), [xxx]	[xx.xx, xx.xx] [xx.xx, xx.xx] [xx.xx, xx.xx]	xxx(xx.xx), [xxx] xxx(xx.xx), [xxx] xxx(xx.xx), [xxx]	[xx.xx, xx.xx] [xx.xx, xx.xx] [xx.xx, xx.xx]
Total	xxx(xx.xx), [xxx]	[xx.xx, xx.xx]	xxx(xx.xx), [xxx]	[xx.xx, xx.xx]

[§]Overlapped, MedDRA latest version

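### The protocol assigns an open adverse event question to first-time users only; for patients already on INLYTA it names just the chart, even after enrolment, so the Table 8 columns are not like for like

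*Protocol*

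**What the plan says.** Protocol 3.1 states that "the study is being conducted in prospective study design and retrospective study design". Section 3.5.4.9.1 then gives the query pattern for adverse events by group:

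- **First-time users** are asked "Have you had any health problem since last visit".
- **Patients already on INLYTA at enrolment**: "all safety information will be collected from medical chart since the date of treatment initiation".

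The same section puts a general duty on both groups: "Every observed and reported adverse event, regardless of the causal relationship with the study drug, must be recorded on an adverse event section". Section 3.5.4 adds that "Data for patients who are currently on INLYTA® will be collected as much as possible following the categories" used for first-time users.

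Three provisions show that patients already on the drug can be followed forward. Inclusion criterion 3 requires signed consent from everyone. Section 5.1.2 starts their safety reporting period at "the time of the patient's informed consent if s/he is already exposed to Inlyta" and runs it to the end of observation. SAP 3.1 removes from the safety set "Subjects who have been already completed for INLYTA® prior to the contract date", so those who remain had not finished treatment before the contract.

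SAP 6.2(1) asks for crude incidence with a 95% confidence interval. Table 8 ("Summary of incidence of adverse events") has columns for Sub-group 1, Sub-group 2 and Total, and SAP 6.4 repeats the main safety analyses by sub-group. Nothing in the SAP tables marks how an event was found, and the limitations in Protocol 3.12 do not mention it.

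**The concern.** An open question brings out events that a patient would not volunteer or a clinician would not write down. A chart contains only what was noted. If one group is asked and the other is read from notes, a difference in recorded incidence can come from the method alone.

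Monitoring adverse events is the core of the study objective, and Table 8 is where the reader will look. A lower figure in Sub-group 2 could be taken for better tolerance among continuing users, and the Total would depend on the mix of the two groups. Pooled Table 24 also tests incidence by duration of administration without listing sub-group as a factor. Duration may be entangled with detection method there.

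The issue is how events are found, not the date from which they count.

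**Working it through.** **Text check.** Four questions decide the point.

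1. *Does the chart rule stop at enrolment?* No. It gives a starting point (treatment initiation) and covers all safety information, with no end.
2. *Does any other section assign a question to these patients?* No. The general recording duty in 3.5.4.9.1 and the 24-hour reporting duty in 5.1.1 apply once an event has surfaced. Section 3.5.4 speaks of categories of data, not of how events are elicited.
3. *Could these patients be asked?* Yes, while they remain in follow-up. They have consented, their reporting period runs forward from consent, and 3.1 has observation continuing during treatment.
4. *Does the SAP separate the methods?* Only in part. It separates the sub-groups, but the boundaries differ. The protocol's chart rule turns on being on the drug at enrolment. SAP 3.4 defines Sub-group 1 by the study period and Sub-group 2 by the contract date. A patient who started after the contract and enrolled later falls under the chart rule yet sits in Sub-group 1. Each column therefore rests mainly, not wholly, on one method, and the Total rests on both.

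**Illustration of size.** The plan has no figure to reproduce: the minimum of 100 subjects in Protocol 3.6 is a regulator's decision with no rate or precision behind it. All inputs below are assumptions, not taken from the documents:

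- p: true incidence, equal in both groups
- s: chart capture relative to asking
- w: share of patients in Sub-group 2

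Sub-group 1 records p and Sub-group 2 records p × s. The gap is p × (1 − s), and the Total is p × [1 − w × (1 − s)].

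| p | s | Sub-group 2 | Gap (points) | Total at w = 0.5 |
|---|---|---|---|---|
| 0.30 | 0.5 | 0.30 × 0.5 = 15% | 15 | (30 + 15)/2 = 22.5% |
| 0.30 | 0.8 | 0.30 × 0.8 = 24% | 6 | (30 + 24)/2 = 27% |
| 0.30 | 0.9 | 0.30 × 0.9 = 27% | 3 | (30 + 27)/2 = 28.5% |
| 0.60 | 0.7 | 0.60 × 0.7 = 42% | 18 | (60 + 42)/2 = 51% |

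The mix matters too. At p = 0.30 and s = 0.5, the Total is 0.30 × (1 − 0.25 × 0.5) = 26.25% with a quarter of patients in Sub-group 2, and 0.30 × (1 − 0.75 × 0.5) = 18.75% with three quarters.

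**What a change could remove.** The table applies s to all of Sub-group 2's time. Let f be the share of Sub-group 2's events with onset after enrolment. If those were found by asking, Sub-group 2 would record p × [(1 − f) × s + f]. The part of the gap removed is p × f × (1 − s). For p = 0.30 and s = 0.5 to 0.8 this is f × 15 down to f × 6 points: nothing if f = 0, and the full 6-15 only if f = 1. The documents do not give f.

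**The case against.** The chart sentence can be read as a look-back rule for patients whose treatment began before enrolment. It does not say that nothing else may be used. Protocol 3.3 and 3.4 name the medical record as the adverse event source for every patient, and 3.7.1 says that the CRF must match the chart where the chart is the source. No visits or activities are mandated for anyone. On this view the groups differ by one open question. The sub-groups are already reported separately, and the SAP plans no test of one against the other. Sub-group 2 also differs in exposure and in having stayed on treatment, so a gap could have other causes.

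Much of this stands, and it limits the point. A reader might infer that patients already on INLYTA are followed by chart alone after enrolment. The text does not go that far: it names no other method, but it forbids none. Nor is each sub-group column a mixture by design; the clear pooling is in the Total. The protocol also does not state how often first-time users are asked, beyond the reference to the last visit.

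It does not remove the point. A shared record source does not equalise what gets into the record when only one group is assigned a question. Separate columns help only a reader who knows that the methods differ.

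**Conclusion.** The plan specifies active questioning for one group and only the chart for the other, including the time after enrolment when both could be asked. Followed as written, it creates an avoidable difference in detection. The Table 8 sub-group columns are then not like for like, and the Total pools two methods.

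Neither the size nor the direction of the effect can be read from the documents. The 6-15 points rest on an assumed 30% incidence and 50-80% relative capture. They are the upper end for those inputs, because they include time before enrolment. Lower recording from charts is itself an assumption, and crude incidence over unequal exposure could offset or reverse it.

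A reader might go on to infer that Sub-group 1 should become the main incidence estimate. The documents do not support that: Protocol 3.5.4.1 and 3.9.2 call for analysis of both groups and of all enrolled patients. The point merits correction but does not invalidate the planned analyses.

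**What to change.** 1. **Protocol 3.5.4.9.1:** state that patients already on INLYTA are asked the same open question at routine visits from enrolment onward, and that chart review covers the time before enrolment.
2. **SAP 6.2(1) and Table 8:** show Sub-group 2 events by onset before and after enrolment. Note that the two windows differ in length, so their crude incidences are not directly comparable. Because onset dates may be approximate, say how an event that cannot be placed is shown.
3. **Table 8 footnote and Protocol 3.12:** state how events were found in each group, and list the difference as a limitation.

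Keep the sub-group and all-enrolled analyses as they are.

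The cost is one protocol sentence, a split column, a footnote and a small amount of CRF work; no visits are added. The downside is that asking helps only patients still in follow-up, and the final report is due on 21 November 2021. If few such patients remain, the split, footnote and limitation still tell the reader how to interpret the columns.
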